## 1.0 Research Design

### 1.1 Purpose/Specific Aims

To determine if the novel combination of salicylic-salicylic acid (Salsalate), venetoclax and decitabine (or alternate hypomethylating agent [HMA], 5-azacytidine] should be developed as a therapy for patients with advanced myeloid malignancies [acute myelogenous leukemia (AML); high risk myelodysplasia (MDS); or high risk chronic myeloproliferative disease] who are not candidates for standard induction chemotherapy with anthracycline + cytarabine. This is a phase 2 study to determine if the novel combination therapy is tolerated well and if biological endpoints are met. There is no control group.

#### A. Objectives

Primary Objective: Determine the tolerability of the addition of standard dose Salsalate to the standard treatment combination of venetoclax + HMA (decitabine or 5-azacytidine).

Secondary Objective: Determine the remission rate and, when feasible, perform exploratory studies of: (i) patterns of mutation clearance; and (ii) distribution of cells with low and high reactive oxygen species (ROS) content at various points during therapy.

#### B. Hypotheses / Research Question(s)

Salicylate has been studied at [REDACTED] as an adjunct to standard AML induction chemotherapy. In those studies, salicylate, administered as choline magnesium trisalicylate was shown to inhibit the expression of the transcription factor nuclear factor kappa-B (NF- $\kappa$ B) in the nucleus of AML cells. The salicylate was also shown to modulate the expression of NF- $\kappa$ B modulated genes, including XIAP, an inhibitor of apoptosis. (1,2). Salicylates are also known to inhibit mitochondrial oxidative phosphorylation, an effect that is anticipated to enhance the anti-leukemic effect of venetoclax (3,5,6,7,9,10). There were no adverse effects associated with choline magnesium trisalicylate in our studies when administered with standard induction chemotherapy (1,2). Other forms of non-acetylated salicylates have also been administered to patients with myeloid malignancies (8). The safety of salicylates in combination with the induction of enhanced expression of anti-apoptotic genes and the uncoupling of oxidative phosphorylation make them an excellent candidate for study in combination with venetoclax + decitabine or 5-azacytidine, a newly approved therapy for patients with AML who are not candidates for standard induction chemotherapy. Our primary hypothesis is that the combination of a salicylate + venetoclax + decitabine (or in selected patients previously treated with decitabine, 5-azacytidine) will be well tolerated and, if so, should be studied further as therapy for advanced myeloid malignancies. We propose to use salicylic-salicylic acid (Salsalate) in this study because our previously performed study used a salicylate, choline magnesium trisalicylate, which is no longer commercially available. Salsalate (salicylsalicylic acid) is composed of two molecules of salicylic acid joined by an ester link. The ester bond of salsalate occurs at the carboxyl group of one salicylic acid molecule and the hydroxyl group of another. Salsalate is non-acetylated so has no effect on platelet function (8). It is used in the treatment of osteoarthritis, rheumatoid arthritis, and other

inflammatory conditions. It has fewer gastrointestinal effects than aspirin and is often used as an anti-pyretic for patients receiving chemotherapy.

Salicylate inhibits expression of some nuclear factor kappa-B regulated genes, like XIAP (2). Salicylates also inhibit oxidative phosphorylation (6,7,9). Our secondary hypothesis is that a salicylate in combination with venetoclax + HMA will result in enhanced cytotoxicity to a subset of malignant myeloid cells with low ROS. In patients with AML, this population is reported to be enriched in leukemic stem cells and the prime target of venetoclax (3,10,12). In exploratory studies we will correspond the survival of these cells with disease response and also patterns of myeloid mutation clearance.

## 1.2 Research Significance

The average age at AML diagnosis is 66 years old. Patients over age 60 with newly diagnosed AML have <20% 3 year survival. Standard cytotoxic induction therapies used in younger patients are often not beneficial when administered to older patients because of intrinsic differences in AML biology in older patients and poor tolerance (based upon age-related co-morbidities). Therefore, patients over age 60 are often treated with lower intensity therapies such as hypomethylating agents like 5-azacytidine or decitabine. These agents yield AML response rates of 20-40%, require 3-5 months to reach best response, and are not curative (11).

Venetoclax is a selective oral inhibitor of bcl-2 and has been developed as component of induction therapy for elderly patients with AML. Bcl-2 is overexpressed in AML cells and leukemic stem cells (the self-renewing component of the leukemia population). The leukemic stem cells show also a high dependence on oxidative phosphorylation and are often sensitive to bcl-2 inhibition *ex vivo*. Several clinical trials of HMAs (or low dose cytarabine) + venetoclax have been reported and these combinations are now approved by the FDA for AML patients not eligible for intensive induction therapy (3,10,12,21,19).

One recently reported multi-institutional dose escalation study combined a hypomethylating agent (5-azacytidine or decitabine) with venetoclax as therapy for AML patients aged 65 years or older. There were 145 patients treated and median age was 74 years old. Approximately 50% had cytogenetic alterations that are labeled high-risk by a consensus panel (European Leukemia Net). Patients with high-risk cytogenetics generally have low remission rates and durations of response, even with aggressive cytotoxic induction therapy followed by allogeneic hematopoietic stem cell transplant. The CR + CRi (complete remission with incomplete blood count recovery) was 69%. The CR + CRi rate was 73% in the cohort receiving venetoclax 400 mg/d. Patients with high-risk cytogenetics obtained CR + CRi of 60% but duration of response in this group was only 6.7 mos compared to 12.3 mos for patients with intermediate risk cytogenetics. CR + CRi rates of 47% were noted in patients with TP53 mutations. Flt3 mutations did not predict outcome and NPM1 mutations were associated with statistically favorable remission rates and durations of response. Neither age >75 nor secondary AML were adverse prognostic features for obtaining CR + CRi. Overall median duration of response was > 11 months with median OS of 17.5 months. In these studies grade 3 adverse events included fever + neutropenia (43%), thrombocytopenia (24%), bacteremia (8%), and pneumonia (13%)(19,20).

Another clinical trial of combination decitabine + venetoclax was presented recently at the 2018 American Society of Hematology Meeting (abstract 286 Maiti et al. Interim Analysis of Phase II Study of Venetoclax with 10-Day Decitabine in Acute Myeloid Leukemia and Myelodysplastic Syndrome. American Society of Hematology 2018). In that study, a prolonged course of decitabine (10 days/cycle as opposed to the standard 5 days/course) was used in combination with venetoclax. Treated patients included elderly patients with newly diagnosed or relapsed/refractory AML. CR + CRi rates for *de novo* AML, secondary AML and relapsed/refractory AML patients were 91%, 72% and 44% respectively. Patients with relapsed/refractory AML had a median duration of response of only ~3 months; patients with *de novo* or secondary AML had median durations of response that exceeded the 12 month period of monitoring.

Both of these studies indicated rapid response rates with best response usually seen by 1-2 cycles of treatment. Both studies also tested for measurable residual disease (MRD). As seen with standard AML therapy, there appeared to be improved response duration in the subset of patients reaching a state of undetectable MRD. In patients treated at the University of Colorado, 22 patients had molecular determination of MRD and 4 had no detectable MRD; none of the 4 with no MRD had relapsed at median f/u > 2 years (5).

These and other studies of older patients with AML indicate that treatment with a HMA in combination with venetoclax can be very effective. Comparison to historic controls treated with standard chemotherapy or single agent hypomethylating agent much improved CR rates and duration of response compared were seen. Even those with traditionally high-risk mutation profiles, secondary AML or age > 75 years old seem to benefit greatly compared to historic controls. However, elderly AML patients with high-risk cytogenetics, relapsed/refractory disease, or prior HMA exposure will have lower CR + CRi rates and durations of response. Even those with newly diagnosed disease who respond are likely to relapse within 2 years. Therefore, modifications of this regimen need to be tested.

Mechanistic studies indicate that leukemic stem cells (the self-renewing population of AML cells) are very dependent on oxidative phosphorylation. It has also been shown that the beneficial effect of venetoclax may in part be based upon this dependence. Well-tolerated drugs known to impact oxidative phosphorylation and/or apoptosis are logical choices for addition to HMAs + venetoclax (3,5,10).

Salsalate is our choice to test in combination with a hypomethylating agent + venetoclax. Salicylates are known to inhibit oxidative phosphorylation and previous clinical trials at Rutgers-CINJ have utilized a salicylate as part of anti-leukemic therapy (1,2,6,7). Choline magnesium trisalicylate used in prior studies is no longer available commercially. In this study we will utilize salicylic acid (Salsalate) at a standard dose. The dose has been shown to result in therapeutic salicylate levels and like the choline magnesium trisalicylate is not acetylated and will not result in platelet dysfunction. This medication is often used as part of supportive care (anti-pyretic) during AML induction chemotherapy. We have shown previously that salicylate modulates the expression of many genes in the WNT and NF-kB pathways, including XIAP, an inhibitor of apoptosis (2). It has also been shown by others that salicylates have a direct mitochondrial effect that impedes oxidative phosphorylation (6,7). In this context, we will study Salsalate in combination with decitabine and

venetoclax as induction therapy for selected elderly patients with advanced myeloid malignancies such as AML, myelodysplasia (MDS) or myeloproliferative diseases with > 10% blast or blast equivalents. Patients who have received decitabine previously will be treated with 5-azacytidine as the HMA. Morphology, standard flow cytometry and next generation sequencing will be used as markers of MRD. When available, single cell DNA sequencing will be used to determine the sensitivity of individual leukemia clones to treatment. Oxidative phosphorylation status of cells will be profiled by flow cytometry to determine if response rates correspond with changes in the profile of oxidative phosphorylation and if Salsalate has independent effects on the profile.

### 1.3 Research Design and Methods

#### A. Research Procedures

In this study we will treat patients with AML, MDS and advanced myeloproliferative disorders with decitabine, venetoclax and salsalate. 5-azacytidine may be substituted for decitabine if the patient has been previously treated with decitabine. Patients will be hospitalized for initiation of therapy (for at least 4 days). Venetoclax dose escalation in cycle 1 will follow the recommended “ramp up” to minimize the risk of tumor lysis. Salsalate will be added on day 5 of decitabine + venetoclax (or 5-azacytidine). There will be only one cycles of treatment with salsalate. The next treatment cycle will be administered under the direction of the treating physician.

Cycle 1:

- i. Venetoclax and decitabine (or 5-azacytidine) will initiate concurrently on d1; salsalate will be start on d5.
  1. Decitabine 20 mg/m^2/d IV will be administered d1-10. If 5-azacytidine is being used (if the patient has previously been exposed to decitabine) it will be administered at 75 mg/m^2/d SC or IV d1-7.
  2. Venetoclax will be dose escalated per package insert - 100 mg d1; 200 mg d2; and 400 mg d3-28.
  3. Salsalate 1500 mg PO bid will start on day 5 of decitabine (or 5-azacytidine) and be administered until and including the day of completion of the decitabine or 5-azacytidine.

Patients with WBC greater than 25,000/uL will be treated with hydroxyurea 2-3g PO bid per treating physician to obtain a WBC<15,000/uL. Once WBC is in target range the protocol treatment can be started. Hydroxyurea may be continued to sustain WBC < 15,000/uL as needed. Standard tumor lysis monitoring and prophylaxis will be used. Allopurinol (or alternate hypouricemic agent) will be started  $\geq$ 24 h prior to starting venetoclax and continued through dose escalation of venetoclax, or longer, as clinically indicated. During dose escalation of venetoclax patients will receive IV fluids, and tumor lysis laboratory studies (basic chemistry profile including calcium, phosphate, uric acid and lactate dehydrogenase) will be obtained every 8 hours.

Infectious disease prophylaxis may be used at the discretion of the patients treating physician. If anti-fungal prophylaxis is used the dose of venetoclax will be modified as outlined below. Proton pump inhibitors are mandated unless there is a contraindication. Venetoclax dosing will be adjusted if concurrent anti-infectives are CYP3A4 or Pgp inhibitors (see below).

Venetoclax dosing will be modified in the context of concurrent use of CYP3A4 or Pgp inhibitors. Venetoclax will be dosed at 70mg /d (if concurrent posaconazole) or 100 mg/d if there is concurrent use of other strong CYP3A4 inhibitors or 200 mg/d if use of moderate CYP3A4 inhibitors. Venetoclax will be dosed at 200 mg/d in the setting of concurrent use of moderate CYP3A4 inhibitors. Dosage should be modified and timing of dose adjusted if concurrent PgtP inhibitors are used. All concurrent meds will be reviewed and dosing schedules approved by a research pharmacist.

**TABLE 1** Commonly used CYP3A4 inhibitors

Moderate	Strong
Aprepitant	Clarithromycin
Cimetidine	Itraconazole
Cyclosporine	Ketoconazole
Erythromycin	Voriconazole
Fluconazole	Posaconazole
Verapamil	Ritonavir
Isavuconazole	Darunavir
Diltiazem	Atazanavir

If the patient has profound thrombocytopenia (< 10,000/uL at day 21 – 28 in the first cycle) a BM asp and biopsy may be performed at the discretion of the treating physician with the option to hold venetoclax. The start of the second cycle is at the discretion of the treating physician and may include modifications of decitabine/5-azacytidine or venetoclax dosing as per standard recommendations. These additional cycles (starting at cycle 2 are not considered part of this clinical trial).

Any Grade 3 or 4 non-hematologic adverse event thought to be Salsalate-related will require the dose to be held until the event recovers to Grade 2 or less. If the adverse event does not resolve within 1 week, the patient will be removed from the study. For Salsalate these events include renal insufficiency, gastritis, tinnitus, vertigo and unanticipated GI bleeding as common toxicities; the Salsalate-relatedness of other toxicities will be assessed by the research team in real time.

Patients will receive full supportive care therapies per Leukemia Tumor Study Group practices concomitantly during the study. No other chemotherapy, immunotherapy, hormonal cancer therapy, radiation therapy, surgery for cancer, or experimental medications will be permitted while the patients are participating in the treatment component of this study (first 2 cycles).

CSFs are not permitted as primary prophylactics. If, in the investigator's opinion, it is required in the presence of severe neutropenia (ANC <500/ $\mu$ l for at least 3 days or concurrent neutropenia and infection) then use of CSFs is allowed per treatment plan described above.

Patients that are not hospitalized will be asked to keep a medication diary and instructed to record the number of capsules taken and the time taken. At the end of each cycle of treatment, the actual amount of unused drug will be compared to the amount taken as recorded on the subject's medication diary.

All patients who receive one dose of protocol therapy will be evaluable for assessment of toxicity. Prior to each cycle the treating physician will fully assess the patient's condition with respect to possible treatment related toxicities. All adverse events, whether observed by the physician or reported by the patient, occurring during the active portion of therapy, or up to 30 days after the last dose of treatment will be graded by a numerical score according to the NCI's Common Terminology Criteria for Adverse Events (CTCAE), Version 5.0 (<http://ctep.cancer.gov/reporting/ctc.html>) and recorded in the patient's medical record. For the purposes of reporting laboratory abnormalities, only Grade 3-4 adverse events will be recorded on the adverse event CRF pages. Grade 1-2 laboratory abnormalities will not be recorded on the adverse event CRF pages. Information entered on the adverse event CRF pages will include:

- Specific type and duration of reaction (i.e., start and stop dates, resolution).
- Severity/grade.
- Relationship to study drug (causality, attribution).
- Management of the event, if treated with medication and other actions taken to alleviate the clinical event.
- Whether or not it was considered a SAE.

A preexisting condition is one that is present at the start of the study. A preexisting condition will be recorded as an adverse event if the frequency, intensity, or the character of the condition worsens during the study period.

An adverse experience is defined as any unintended or abnormal clinical observation that is not of benefit to the patient. Either the condition was not present prior to exposure to the study therapy, or it has worsened in intensity or frequency following exposure to the study therapy.

All "unexpected" (defined below) and/or "serious" experimental drug related adverse events occurring during the active portion of therapy, or up to 30 days after the last dose of treatment, will be reported to the Office of Human Research Services at [contact] or [contact]. Events will be promptly reported, in writing, to the local IRB in accordance with IRB policy. If a death occurs the IRB will be notified within 24-hours of initial receipt of information. All other SAEs must be reported to the IRB within three to ten days of initial receipt of information. Written follow-up reports are required when additional information is needed to fully characterize the event. Copies of each report sent to the IRB will be kept in the study regulatory file.

In addition to reporting to the local IRB, reporting to external bodies such as industry and/or the FDA may be necessary

In the absence of treatment delays due to adverse events, treatment may continue until one of the following criteria applies:

- a) Disease progression/relapse during active treatment,
- b) Intercurrent illness that prevents further administration of treatment,
- c) Unacceptable adverse event(s).
- d) In the event of any drug-related life-threatening toxicity or laboratory abnormality the patient will be withdrawn from further treatment,
- e) Patient decides to withdraw from the study,
- f) Noncompliance with treatment plan,
- g) General or specific changes in the patient's condition render the patient unacceptable for further treatment in the judgment of the investigator, or
- h) Protocol violation - any patient found to have entered this study in violation of the protocol might be discontinued from the study at the discretion of the Principal Investigator.
- i) The desired level of compliance is  $\geq 75\%$ . Patients who cannot maintain this level of compliance may be removed from the study.

Evaluations	Pre-Study (within 2 weeks)	Daily during treatment with decitabine or 5-azacytidine	Prior to Next Treatment
Initial History & Physical	X		
Interim History & Physical		X while hospitalized	X
Toxicity Assessment		X	X
Concomitant Medications	X	X	X
ECOG Performance Status	X		X

CBC, differential, platelets	X 	X while hospitalized	X
Serum Chemistries 	X	X while hospitalized	X
Tumor lysis monitoring and treatment)		X (q8h during ramp up and qd while hospitalized)	
Liver Enzymes 	X	X while hospitalized	X
EKG	X		
Pregnancy Test 	X		X
Radiographic Assessments 	X		
REDOX Blood Studies  (during first week of treatment)	X	X (pre first dose of salsalate and after 4-8 doses salsalate based on blood counts)	
BM asp and biopsy	X		X 
Blood flow cytometry/NGS (next generation sequencing) 	X	X	
Compliance Assessment			X
Survival 			

- |  |  |
|--|--|
| 
 
1. Within 1 week of enrollment.
 
2. Includes: Electrolytes, Calcium, BUN, Creatinine, Total Protein, Glucose, Albumin, Total Bilirubin, Alk. Phosphatase, SGOT/SGPT.
 
3. Includes: Total and Direct. Bilirubin, AST/ALT, Alkaline Phosphatase, Albumin, Total Protein.
 
4. Women of childbearing potential must have pregnancy test verified by BHCG within 1 week of enrollment.
 
5. Radiographic assessments will be selected by the attending physician as clinically indicated and in accordance with the criteria for tumor measurement assessments.
 
6. REDOX analysis ([name] lab) will be done on blood samples with CD34 selected blasts at baseline, after 1-5 days of treatment and following administration of of Salsalate with exact timing determined by numbers of leukemic blasts in the blood
 
7. NGS from BM will be done at baseline and after the second cycle or on any BM with leukemic cells detected as performed for clinical reasons. NGS or Single cell DNA sequencing may also be done by [name] as feasible from blood based upon disease status and resources.
 
8. Subjects will be tracked until relapse or change of therapy.
 
9. Disease status and survival status will be documented every 2 months until disease progression or start of new treatment.
 
10. End of Treatment = 45 days after the last dose of Salsalate.
 
11. Bone marrow aspirate can be performed within 14 days of anticipated next treatment cycle.
 
 |  |
|--|--|

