**D. Endpoints**

Primary endpoint: For testing the primary hypothesis, the toxicity of salicylate + venetoclax + decitabine during the first two cycles will be collected as primary endpoints.

Secondary endpoint: We will correspond response rates with the pattern of survival of low oxygen reactive species cells. The administration of drugs will be timed to determine if there is a measurable added effect of salicylate on the oxidative state of cells when used in combination with venetoclax + decitabine. Next generation sequencing will determine also if there is a correspondence of remission with patterns of mutation clearance and/or effects of treatment on the oxidative state of the leukemia cells.

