#### **6.0 Data Management Plan**

##### **6.1 Data Analysis**

1. An unacceptable adverse event is defined as a Grade 3 study drug (SALSALATE) related or possibly related irreversible (i.e. doesn't reverse within one week) event with the exception of:
  - a. Grade 3 fever, asthenia or constipation.
  - b. Grade 3 nausea, vomiting, diarrhea (not requiring tube feeding, total parenteral nutrition, or prolonged hospitalization;
  - c. Grade 3 infection, bleeding or expected complications of cytopenias due to leukemia or decitabine + venetoclax treatment;
  - d. Grade 3 or 4 tumor lysis syndrome successfully managed clinically that resolves within 7 days without end organ damage; or
  - e. Grade 3 or 4 isolated electrolyte abnormalities that last < 72 hours.

We consider an adverse event rate of 7% or higher to be unacceptably high, so we will stop the trial if, at any point, we are 80% certain that the rate is 7% or higher. In the following table, the shaded cells in the table indicate the region where we are 80% certain that the rate exceeds 7%.

According to this table, if there is 1 unacceptable (grade 3) SALSALATE related or possibly related adverse event (defined above) among the first 10 patients, or if there are 2 unacceptable adverse events among the first 20 patients, the trial will be stopped for unacceptable toxicity.

This table was calculated using a Bayesian posterior beta distribution, assuming a uniform prior.

N patients      k: number of unacceptable toxicities

	0	1	2	3
3	0.748052	0.973272	0.9987	0.999976
4	0.695688	0.957507	0.99692	0.999887
5	0.64699	0.939179	0.994161	0.999679
6	0.601701	0.918726	0.990312	0.999293
7	0.559582	0.896534	0.985301	0.998664
8	0.520411	0.872948	0.979088	0.997729
9	0.483982	0.84827	0.971658	0.996424
10	0.450104	0.82277	0.963021	0.99469
11	0.418596	0.796683	0.953203	0.992473
12	0.389295	0.770217	0.942247	0.989724
13	0.362044	0.743553	0.930205	0.986401
14	0.336701	0.716847	0.917139	0.982467
15	0.313132	0.690237	0.903119	0.977894
16	0.291213	0.663839	0.888217	0.97266
17	0.270828	0.637756	0.87251	0.966749
18	0.25187	0.612071	0.856078	0.960152
19	0.234239	0.586857	0.838997	0.952867
20	0.217842	0.562173	0.821347	0.944896

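### Section 1.3 A does not separate stopping treatment from leaving the study when a Salsalate toxicity persists for a week, so response and later safety data may be lost in patients selected by toxicity

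*Combined protocol and SAP*

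**What the plan says.** **The removal rule.** Section 1.3 A first sets a hold, with recovery to at most Grade 2 as its threshold: "Any Grade 3 or 4 non-hematologic adverse event thought to be Salsalate-related will require the dose to be held until the event recovers to Grade". The sentence after it adds: "If the adverse event does not resolve within 1 week, the patient will be removed from the study".

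**The counted event.** Section 6.1 defines the unacceptable adverse event by the same one-week feature. It is a Grade 3 Salsalate "related or possibly related irreversible (i.e. doesn't reverse within one week) event with the exception of" five listed categories.

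**Treatment-only wording.** The list of discontinuation criteria in section 1.3 A deals with unacceptable events in item c and drug-related life-threatening toxicity in item d. Both end treatment, and neither says that the patient leaves the study.

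**Toxicity data.** Section 1.3 A says: "All patients who receive one dose of protocol therapy will be evaluable for assessment of toxicity". Adverse events "occurring during the active portion of therapy, or up to 30 days after the last dose of treatment will be graded", and the case report form records their duration and resolution. The primary endpoint in section 1.3 D is wider than the section 6.1 event: "the toxicity of salicylate + venetoclax + decitabine during the first two cycles will be collected as primary endpoints".

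**Follow-up and response.** Footnotes 8 and 9 to the evaluation table in section 1.3 A track patients up to relapse or a switch in therapy, with disease and survival status every two months. Footnote 11 allows the marrow within 14 days of the expected next cycle. Section 1.1 A gives "Secondary Objective: Determine the remission rate". No section gives the denominator for that rate or a rule for a missing response, or says whether a removed patient still has the marrow.

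**The concern.** The rule speaks of the study, not of Salsalate, and its trigger is a toxicity outcome. If it is followed as written, patients leave because of how their toxicity behaved, and what is not yet collected on them goes missing for that reason. Two things are at stake.

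- **Remission rate.** If patients with persistent toxicity remit less often than others, leaving them out raises the reported rate. Section 1.5 says the data are meant to support a larger randomized trial, so this figure will be used.
- **Later safety course.** How a toxicity that did not reverse in a week finally ends is useful information in a tolerability study. The two-cycle toxicity endpoint also runs past the point of removal.

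**Working it through.** **1. When the rule acts.** Section 1.3 A gives Salsalate from day 5 to the last day of the hypomethylating agent, which is day 10 with decitabine and day 7 with 5-azacytidine. For an event that starts on a dosing day, removal falls at onset + 7 days:

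- earliest: 5 + 7 = day 12;
- latest with decitabine: 10 + 7 = day 17;
- latest with 5-azacytidine: 7 + 7 = day 14.

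All of these lie after the last planned Salsalate dose. On the planned schedule the rule therefore has no Salsalate left to stop, and what remains is its effect on participation.

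**2. What is still to come.** Assume a 28-day cycle, since venetoclax is planned to day 28. The 14-day marrow window is then about day 14 to 28. Removal on day 12 to 17 comes before the window or early in it, so the marrow and the visit before cycle 2 usually lie ahead. If the 30-day adverse-event window is counted from a last Salsalate dose on day 10, it closes on day 40. A second 28-day cycle would run from about day 29 to 56.

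**3. Who is removed.** The two definitions overlap but differ.

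- The removal rule names Grade 3 or 4 and has no list of exceptions. Section 6.1 opens with Grade 3, although two of its exceptions mention Grade 4.
- The removal rule needs an event thought to be related. Section 6.1 also takes possibly related events.
- The exempt tumor lysis and electrolyte events in section 6.1 are limited to 7 days and under 72 hours, so they should not reach the one-week trigger.
- Events that could lead to removal without being counted are mainly persistent Grade 3 fever, asthenia, constipation or gastrointestinal symptoms attributed to Salsalate. The documents give no frequency for these.

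**4. The stopping rule.** The section 6.1 table is the posterior probability that the rate exceeds 7%, under Beta(k + 1, n − k + 1) from a uniform prior. Nine cells were recalculated and all agree to six decimals. At the boundaries:

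- 1 event in 10: 0.82277, as printed;
- 2 events in 20: 0.821347, as printed.

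If removed patients left the toxicity set, these would fall to 0.484 (0 of 9) and 0.252 (0 of 18), and the rule would not be met. The one-dose evaluability sentence excludes that. The counted event is also complete at removal, taking resolution in section 1.3 A and reversal in section 6.1 to mean the same thing.

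**5. How many counted events.** The rule was applied after each patient from the third on, assuming that each is assessed before the next enrols. At a true rate of 7%, the probabilities of ending with 0, 1 or 2 counted events are 0.234, 0.678 and 0.087. Three or more has probability 0.008 even at a true rate of 20%. Uncounted removals would add to these.

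**6. Effect on the remission rate.** With r unassessed patients of 20, the gap between all and none of them remitting is r/20: 5 points for 1, 10 for 2, 15 for 3. As an illustration, take 2 unassessed and an observed rate near the 69% that section 1.2 cites for venetoclax with a hypomethylating agent. Then 0.69 × 18 = 12.4, or 12 remissions among the 18 assessed:

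| Handling of the 2 unassessed | Rate |
|---|---|
| Dropped | 12/18 = 66.7% |
| Counted as not in remission | 12/20 = 60% |
| Both remitted | 14/20 = 70% |

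**The case against.** The strongest reply is that nothing says data collection stops. Adverse events are graded to 30 days after the last dose, with resolution recorded. Written follow-up reports are required where a reportable event needs fuller description. Tracking and two-monthly status checks carry no exception. Footnote 10 ties the end of treatment to 45 days after the last Salsalate dose, not to completing the cycle. Section 6.3 A includes best response among the off-treatment data. A generous reader could conclude that removal means coming off treatment.

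Much of this stands. A reader might infer that the rule cuts follow-up in exactly the patients who have the primary event. The documents do not support that. The primary endpoint is all toxicity over two cycles, the removal group and the section 6.1 group are not the same, and the follow-up provisions make the text inconsistent rather than clearly restrictive.

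The reply does not settle the matter, however. Item d shows that the protocol has treatment-only wording, and the removal sentence does not use it. No section says that a removed patient keeps the visit and marrow before cycle 2, and the one-dose sentence protects toxicity only.

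It is also fair to say that a missing denominator affects every unassessed patient, whatever the reason, and that the remission rate is a descriptive secondary outcome with no test or threshold. This limits the weight of the point.

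**Conclusion.** The point holds as an inconsistency with a modest consequence. The removal sentence conflicts with the treatment-only criteria and the general tracking rules of the same section. Followed literally, it can lose the response marrow and later safety follow-up in patients selected by toxicity. The counted section 6.1 event and the stopping rule are not affected.

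The supportable size is about 5 percentage points of uncertainty in the remission rate per unassessed patient, with 20 treated. It could go either way, because the documents do not say whether patients with persistent toxicity remit less often. This rests on a 28-day cycle, on onset during Salsalate dosing, and on removed patients actually missing the marrow.

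A reader might infer a larger inflation, for example 12/16 = 75% in place of 12/20 = 60%. That needs four removals, all unassessed, all non-remitting and all dropped, in a trial that stops at 1 counted event in the first 10 or 2 in 20. With three or more counted events below 1% under the assumptions above, at least two of the four would almost certainly be events that section 6.1 does not count. The documents give no basis for that.

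**What to change.** Reconcile the removal sentence, the discontinuation criteria and the evaluation-table footnotes in section 1.3 A. No view is taken here on the hold or on the treatment decision, which the change should leave as they are. The amended text should state:

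- that stopping study treatment is separate from leaving the study;
- that a patient who stops for a persistent Salsalate-related event keeps adverse-event follow-up to resolution, the already scheduled visit and marrow before the next cycle, and the two-monthly status checks, unless consent is withdrawn;
- that the remission rate is reported over all treated patients, with unassessed patients counted as not in remission and their number given.

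The cost is a short amendment that touches several places. No visit is added, because these assessments are already on the schedule. The reported remission rate may be slightly lower. The change is best made early, since a marrow missed before cycle 2 cannot be recovered later.
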